***Outcome Measures***

Hemoglobin A1C will be measured via a fingerstick capillary blood collection and analyzed on the Tosoh G8 HPLC. This approach is validated and traceable to DCCT standards.

CGM-derived glycemic metrics. Participants will have the Dexcom G6 Pro (blinded CGM) inserted 1 week after enrollment and at visit 1, and at visit 2. Participants will wear the CGM for 10 days following each insertion. We will consider >120 hours (>50% of total possible capture) of CGM data to be analyzable, otherwise data will be considered missing. Percent time in range (70-180), percent time >180, percent time >250, percent time <70, and percent time <54 mg/dL will be collected.

Participants who already have their own CGM will wear and use it as usual. They will not require a blinded Dexcom.

For patient-reported outcomes, questionnaires may be completed on iPad for in-person visit or via email or text via Twilio for remote visits. If completing by email or text, a link to REDCap will be sent to participant.

Quality of Life will be assessed using the MIND Youth Questionnaire (My-Q), which is a valid measure of quality of life for teenagers with diabetes (49).

Acceptability will be assessed based on treatment satisfaction scores using the Diabetes treatment Satisfaction Questionnaire, DTSQ-Teen, which has been validated for use in youth with T1D (50).

Trust in provider: Will be measured as a change score (visit 2-visit 1; visit 3-visit 1) with 10-items from the validated Wake Forest Physician Trust Scale (58).

Perceived Involvement in Care: Will be measured as a change score (visit 2-visit 1; visit 3-visit 1) with 13-items from the Perceived Involvement in Care Scale (59).

Health-related empowerment: Will be measured as a change score (visit 2-visit 1; visit 3-visit 1) with 8-items from the Health-related empowerment scale (60).

### ***Covariate Measures***

Demographics: Age, sex, race, duration of diabetes.

Depression will be measured as a covariate using the validated PHQ-A (which is the Patient Health Questionnaire, PHQ-9, adapted for adolescents) (51). *Note: no notification of medical personnel is necessary if adolescents endorse depressive symptoms because a) the survey does not ask about current suicidal ideation, and b) adolescents in the Children's Mercy Diabetes Center are monitored for depression symptoms at every clinical encounter, with clinical encounters occurring every 3-4 months typically.*

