#### Study Visits

Study visits may occur in-person or remotely (i.e., from home). Procedures will be adapted to accommodate both scenarios.

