### Participant activities:

Participants enroll in COIN2DOSE	Participants randomized and fill out questionnaires Setting: at regularly scheduled standard of care (SOC) visit, in-person or virtual visit utilizing a CMH IRB approved remote platform.
1 week post enrollment	All groups will have Dexcom sensor inserted and will be worn x 10 days. Setting: in-person at the PCRU or virtual meeting.** Dexcom sensor may be mailed to participants. If mailed, the 1-week visit may take place via virtual visit utilizing a CMH IRB approved remote platform.  Participants with their own CGM will wear it as usual.
3 months post enrollment	Participants fill out questionnaires + have blinded Dexcom sensor inserted during SOC visit or virtual visit. Participants will wear Dexcom x 10 days. Setting: SOC visit, in-person or virtual visit utilizing a CMH IRB approved remote platform.
6 months post enrollment	Participants fill out questionnaires and wear Dexcom x 10 days. Dexcom inserted during SOC visit or virtual visit utilizing a CMH IRB approved remote platform. Setting: clinic or remote visit utilizing a CMH IRB approved remote platform.  Finally, participants return CGM by mail. (Not applicable to participants with their own CGM.)  Focus group discussions are conducted. Both youth and parents will be invited to participate.

\*\*Participants may choose to have in-person Dexcom insertion instruction at the PCRU or online via virtual instruction. If participant is Dexcom naive, they may insert Dexcom for the first time via online instruction, as it is a relatively simple procedure. If a participant is uncomfortable inserting the Dexcom for the first time virtually, they will have the option to do this with in-person instruction at the PCRU.

The link that patients will be sent for learning to use Dexcom is:

<https://www.dexcom.com/training-videos>

Participants with their own CGM will not be anticipated to require training; however, this will be offered if needed.

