## **17.0 Risks to Subjects**

The overall risks of participation in this project are no more than minimal. Because the research requires the collection of personally identifying data, there is a risk breach of confidentiality. Participants will be requested to disclose information about their diabetes adherence, blood glucose values, regimen knowledge, and psychological and behavioral functioning. Disclosing this information may potentially lead to emotional discomfort. If a participant reports any concerning symptoms regarding his or her emotional stature, the participants and his/her parent/guardian will be provided with information on how to get help. If a participant has a positive screen on the PHQ-A (depression), social work will be notified and will see the participant during the study visit. Social work will assess the patient and develop a plan of action in conjunction with the attending physician based on the clinical situation. Participants may also feel inconvenienced by the time required to participate in the study. Participants may

experience some discomfort with Dexcom insertion, which is similar to insulin pump site insertions. Participants will be instructed on proper care of the Dexcom site.

In the virtual focus group discussions, there is minor risk of unauthorized disclosure of confidential information, which would be made known to participants and will be minimized by the research team's efforts to ensure confidentiality (see section 20.0). Every effort will be made to keep data de-identified, including having participants use pseudonyms for the discussion and being reminded not to respond in a way that might include personal identifying information. Risks are greatly reduced by using secure files, storing data on secure computers, de-identification of data. Subjects and/or their parents/legal guardians may choose not to participate in the focus groups. There may be a risk that some of the questions make participants feel uncomfortable. Participants may skip a question or stop the study at any time.

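### Section 4.0 says no one need be told when an adolescent reports depressive symptoms, while Section 17.0 requires a same-visit social-work response to a positive PHQ-A

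*Protocol*

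**What the plan says.** Section 4.0, under Covariate Measures, introduces the PHQ-A as a covariate and adds a note that "no notification of medical personnel is necessary if adolescents endorse depressive symptoms". The note gives two reasons. The first is that "the survey does not ask about current suicidal ideation". The second is that the clinic already monitors its adolescent patients for depression whenever they are seen, "with clinical encounters occurring every 3-4 months typically".

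Section 17.0 (Risks to Subjects) deals with a positive screen on the same instrument. There, "social work will be notified and will see the participant during the study visit", and social work is to assess the patient and "develop a plan of action in conjunction with the attending physician". Section 17.0 also provides that a participant who reports worrying emotional symptoms, and the parent or guardian, receive information on how to get help.

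The schedule of events in Section 10.0 places the depression questionnaire (listed as PHQ9) at visits 1, 2 and 3. Under Outcome Measures, Section 4.0 says that "questionnaires may be completed on iPad for in-person visit or via email or text via Twilio for remote visits". On in-person versus remote visits, Section 6.0 says only that "Procedures will be adapted to accommodate both scenarios".

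**The concern.** The two sections tell staff different things about the same adolescents, the same questionnaire and the same event. One makes a response mandatory at the visit; the other says that telling medical personnel is unnecessary. Someone administering the PHQ-A is likely to look first at the description of the measure, which is where the waiver sits.

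What is at stake is participant safety. The participants are minors, and the social-work assessment is a safeguard that the protocol's own risk section sets out. If the Section 4.0 note is followed, a positive screen may wait for whatever the clinic's routine monitoring picks up at its next encounter. No estimate, error rate or sample size depends on this.

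**Working it through.** There is no stated figure to reproduce. The check is a comparison of texts, followed by simple arithmetic on timing and exposure.

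**Side by side**

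| | Section 4.0, Covariate Measures | Section 17.0 |
|---|---|---|
| Instrument | PHQ-A | PHQ-A |
| Trigger | Depressive symptoms reported | Positive screen |
| Action | Notification not necessary | Social work notified and sees the participant |
| Timing | Left to routine clinic encounters | During the study visit |
| Physician | Not informed | Attending physician shares in the plan |

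**Can the two be reconciled?**

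1. *Social work might not count as medical personnel.* This does not help, because Section 17.0 also brings in the attending physician.
2. *Reporting symptoms might mean answers below the threshold for a positive screen.* A participant with a positive screen has reported symptoms. Section 4.0 carves out no exception, and the protocol gives no PHQ-A cut-off at which one rule would hand over to the other.
3. *One text might supersede the other.* Both are current, neither refers to the other, and the revision history lists no change to either.

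**Timing**

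The response under Section 17.0 comes at the same visit, so the delay is 0 days. Under the Section 4.0 note the fallback is the next clinic encounter. Using the typical interval stated there and 30.4 days per month:

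- 3 × 30.4 = 91 days
- 4 × 30.4 = 122 days

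These are gaps between encounters, so they bound the delay and do not estimate it. For the 3-month visit, Section 10.0 gives "Setting: SOC visit, in-person or virtual visit utilizing a CMH IRB approved remote platform". If the study visit is also a standard-of-care visit, the clinic's own monitoring happens then and the delay can be 0. If it is a separate visit just after a routine encounter, the delay can approach 4 months. The possible range is therefore 0 to about 122 days.

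**Exposure**

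The questionnaire is scheduled at 3 visits, and Section 1.0 gives 36 to 72 youth:

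- 36 × 3 = 108 scheduled administrations
- 72 × 3 = 216 scheduled administrations

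Each of these falls under the conflicting rules. The number that would screen positive cannot be derived from the protocol.

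**The case against.** The strongest reply is that the conflict is softer than it looks. Section 4.0 says notification is not necessary; it does not forbid it. Section 17.0 is mandatory, and staff who follow it comply with both. That is correct, and it means the safeguard exists. It does not make the note harmless, since calling a required step unnecessary invites its omission. That staff would in fact omit it is an inference from the wording; the protocol does not show that they would.

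A second point is that the triggers are worded differently, so the author may have meant a general rule for any symptom and a special rule for a positive screen. That is plausible as intent, but the text does not say it.

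Third, the note's first reason bears on urgency: if the survey does not ask about current suicidal ideation, the note does not waive a response to ideation disclosed on it. Taken at face value this lowers the stakes. It does not cancel Section 17.0, whose trigger is a positive screen and does not depend on suicidal ideation.

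Fourth, there are backstops: routine clinic monitoring, help information for worrying symptoms, and the safety review described in Section 21.0. They are real, but none is a same-visit assessment. Clinic monitoring is periodic, and the review board is to meet every 6 months.

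Finally, a delay near 4 months is a worst case. It needs a positive screen, a study visit away from standard care and a routine encounter only recently past, and the protocol gives no frequency for any of these. That stands, and the conclusion does not rest on the upper figure.

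**Conclusion.** The protocol is wrong as written on this point. Section 4.0 waives, without exception, a notification that Section 17.0 makes mandatory after a positive PHQ-A, and nothing in the protocol reconciles them. If the note is followed, the possible delay runs from 0 to about 122 days, assuming the typical 3-4 month encounter interval holds. The number of participants affected is unknown. The conclusion rests on the conflict in the text; the delay only indicates its possible size. This is a participant-safety defect with no statistical consequence. It should be corrected because it concerns minors and the remedy is very small.

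**What to change.** Let Section 17.0 govern. Delete the note under Covariate Measures in Section 4.0, or replace it with a cross-reference such as: *Every positive PHQ-A screen at visits 1, 2 and 3 is handled as described in Section 17.0.*

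Two additions would make the rule easier to apply, though the correction does not depend on them:

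- State the PHQ-A score that counts as positive.
- For remote visits, say that social work contacts the participant by telehealth or telephone. Remote questionnaires are completed through an emailed or texted REDCap link, and Section 17.0 does not say how social work sees the participant in that case.

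The deletion or cross-reference costs one wording amendment. The remote clause costs somewhat more in practice, since someone must look at remotely submitted scores promptly enough to act on them. Data collection, sample size, power, alpha and the primary analysis stay as they are.

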## **5.0 Study Intervention**

To identify an at-risk population for more intensive intervention opportunities, the Children's Mercy Diabetes Center now routinely uses a validated prediction model based on advanced machine learning (random forest method) and natural language processing to identify individuals who are predicted to experience a rise in A1C in the next 90 days. The model analyzes all patients who presented for a diabetes visit in the prior week. To accomplish this task, the complete health record for the CMH Diabetes Center registry is analyzed. We will select patients from this cohort for recruitment into the present study.

**COIN2DOSE intervention:** From one-week post-randomization to the 12-week study visit, youth randomized to this treatment arm will receive personalized feedback via monetary incentives for dosing insulin at mealtimes. We will define mealtimes based on hour of the day and the presence of a carbohydrate entry associated with the insulin bolus. According to the methodology for calculating BOLUS(1) breakfast will be 0600-1000, lunch will be 1100-1500, and dinner will be 1600-2200. Thus, we will reimburse youth up to \$0.50 per mealtime with at least one meal-associated (carbohydrate-associated) insulin bolus completed (maximum \$1.50/day). We will offer the opportunity for youth to earn a bonus reimbursement of up to \$5.00/week for weeks during which they achieve at least 5 days of 3 mealtime insulin boluses. Finally, we will pay youth up to \$2.00 per week for sharing their insulin use data at least two times per week with the study team during the three-month treatment phase (maximum \$24.00). Therefore, maximum total incentive available is \$210.

**LOAN2DOSE intervention:** From one-week post-randomization to the 12-week study visit, youth randomized to this treatment arm will receive personalized feedback via monetary deductions from a virtual bank of \$210 for missed doses of insulin at mealtimes. Participants will receive a weekly email or text message using Twilio to communicate their current virtual bank balance. We will define mealtimes based on hour of the day and the presence of a carbohydrate entry associated with the insulin bolus. According to the methodology for calculating BOLUS (1) breakfast will be 0600-1000, lunch will be 1100-1500, and dinner will be 1600-2200. Thus, we will deduct \$0.50 per mealtime with at least one meal-associated (carbohydrate-associated) insulin bolus missed (maximum -\$1.50/day). Youth can also lose an additional amount of up to \$5.00/week for weeks during which they don't achieve at least 5 days of 3 mealtime insulin boluses. Finally, we will deduct the virtual account up to \$2.00 per week for failing to share their insulin use data at least two times per week with the study team during the three-month treatment phase (maximum deduction of \$24.00). Therefore, maximum total deductions is \$210.

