## 1.0 Study Summary

Study Title	HCT Cash-Only IN centive to promote mealtime insulin DOSE Engagement (HCT COIN2DOSE): a pilot trial
Study Design	Pilot randomized controlled trial
Primary Objective	To determine the impact of HCTCOIN2DOSE and LOAN2DOSE compared to control on the trajectory of glycemic control and treatment engagement among adolescences age 12-17 years who are at risk for a near-term rise in A1C.
Secondary Objective(s)	To determine both the feasibility and usability of HCTCOIN2DOSE and LOAN2DOSE intervention compared to control in adolescents age 12-17 years who are at risk for a significant near-term rise in A1C.
Research Intervention(s)/ Investigational Agent(s)	HCT COIN2DOSE: Utilization of immediate financial incentives to promote mealtime insulin dose delivery, with weekly bonuses for sustained meal dosing behavior LOAN2DOSE: Utilization of loss aversion approach to promote mealtime insulin dose delivery. Participants will start with a virtual bank balance and will have money deducted from the balance when mealtime insulin doses are missed. Additional amounts will be deducted when sustained meal dosing goals are not met.
IND/IDE #	NA
Study Population	Individuals identified by artificial intelligence who are predicted to experience a rise in A1C of greater than or equal to 0.3% in the next 70-110 days using a validated predictive algorithm created via advanced machine learning (random forest) and natural language processing. Individuals must have had the diagnosis of T1D for 6 months and be 12-17.99 years old. Parents of children who meet inclusion criteria may choose to participate in the focus group
Sample Size	A minimum of 36 and a maximum of 72 youth randomized in a 1:1:1 ratio to either the treatment or usual care (control).  Participants and their parents may choose to participate in the focus group. Parents may enroll in the focus group if their child is enrolled in the study. Our aim will be to enroll 5 to 30 parents.
Study Duration for Individual Participants	26 weeks (11-13 weeks intervention and 11-13 weeks observation Participants and/or their parents may choose to participate in a focus group at the end of the study (week 26).

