## 10.0 Study Timelines

Table 1. Schedule of events

visit #	Visit 1	CGM placement	Intervention	Visit 2	Maintenance	Visit 3
		1 week post enrollment	1-12 week post CGM placement	3 months (+/-14 days)	12 weeks post visit 2	6 months (+/-14 days)
Consent	x					
Randomization	x					
CGM (10-day)		x*		x*		x*
A1C	x			x		x
Demographic	x			x		x
PHQ9	x			x		x
DTSQteen	x			x		x
MyQ	x			x		x
Wake Forest Physician Trust Scale	x			x		x
Perceived Involvement in Care Scale	x			x		x
Health-related empowerment scale.	x			x		x
Concerns about AI	x			x		x
Pump/pen** download	x		x	x	x	x
Focus Group Participation - Youth						x
Focus Group Participation - Parents						x

\*CGM will be returned by pre-paid, registered delivery service with tracking.

\*\* Control: pump/pen upload will occur monthly; COIN2DOSE and LOAN2DOSE pump/pen upload will occur twice weekly.

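### The $210 incentive maximum and LOAN2DOSE bank fit only 12 paid weeks, but Section 5.0's own payment period reads as 11 weeks and other sections give different lengths

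*Protocol*

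**What the plan says.** **Period.** Section 5.0 of the protocol describes COIN2DOSE as running "From one-week post-randomization to the 12-week study visit, youth randomized to this treatment arm will receive personalized feedback via monetary incentives". The LOAN2DOSE paragraph gives the same start and stop for deductions. Other sections describe the period differently:

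- Section 1.0 (Study Summary): "11-13 weeks intervention and 11-13 weeks observation".
- Section 6.0: visit 2 comes after 12 weeks, also given as 90 days, and interventions stop after that visit.
- Section 10.0, Table 1: the intervention is "1-12 week post CGM placement", with CGM placement itself one week after enrolment. Visit 2 is at 3 months with a window of 14 days either way.

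**Amounts.** COIN2DOSE pays $0.50 per mealtime with an "insulin bolus completed (maximum \$1.50/day"). Participants can also "earn a bonus reimbursement of up to \$5.00/week for weeks during which they achieve at least 5 days of 3 mealtime insulin boluses". Data sharing earns up to $2 per week "during the three-month treatment phase (maximum \$24.00"). The stated total is $210.

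LOAN2DOSE opens with a virtual bank of $210 and applies the same rates as deductions. Its paragraph ends "Therefore, maximum total deductions is" $210. Its per-meal deduction applies to a mealtime "with at least one meal-associated (carbohydrate-associated) insulin bolus missed".

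Section 15.0 says the incentive payment is the COIN2DOSE intervention. It repeats $210 for both arms and gives a total of $330 once the $120 for study visits is added.

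**The concern.** Section 5.0 presents $210 as following from the rates and period in the same paragraph. With the period as worded, it does not follow. Three things depend on the answer.

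- **The promised amount.** $210 and $330 are presented as attainable by participants. On an 11-week period, a fully adherent COIN2DOSE participant could not reach either.
- **The consistency of the intervention.** One arm builds up from zero and the other counts down from a fixed sum. Unless the paid period is the one that the fixed sum assumes, identical behaviour pays different amounts in the two active arms.
- **A feasibility outcome.** Secondary outcomes 8 and 12 in Section 4.0 ask whether parents could provide an incentive equivalent to the one used. That amount should be unambiguous.

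**Working it through.** **Inputs (Section 5.0).** $0.50 per mealtime, 3 mealtimes a day; $5.00 weekly bonus; $2.00 a week for data sharing, capped at $24; total $210.

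**Weekly maximum.** 3 × $0.50 × 7 = $10.50; $10.50 + $5.00 + $2.00 = $17.50.

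**Reproducing the plan's figure.** $210 / $17.50 = 12 weeks, and $24 / $2 = 12 weeks. At 12 weeks: $126 meals + $60 bonus + $24 sharing = $210. The figure is exact for 12 paid weeks.

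**The period as worded in Section 5.0.** Week 1 to week 12 is 12 − 1 = 11 weeks: $115.50 + $55 + $22 = $192.50. Added to the $120 for visits, that is $312.50, not $330.

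**Other readings.** Randomization is day 0 and payment starts on day 7. Part-weeks are pro-rated, an assumption, since the protocol does not say how they count. If m is the money forgone (COIN2DOSE) or deducted (LOAN2DOSE) over w weeks, COIN2DOSE pays 17.50w − m and LOAN2DOSE pays 210 − m. The gap is 210 − 17.50w whatever m is, before any cap applies.

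| Visit 2 | Paid days | Weeks | 17.50 × weeks | LOAN2DOSE minus COIN2DOSE |
|---|---|---|---|---|
| Day 76 (90 − 14) | 69 | 9.86 | $172.50 | $37.50 |
| Day 84 (12 weeks) | 77 | 11.00 | $192.50 | $17.50 |
| Day 90 | 83 | 11.86 | $207.50 | $2.50 |
| Day 91 | 84 | 12.00 | $210.00 | $0 |

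If only complete weeks earn the weekly amounts, day 90 gives 83 × $1.50 + 11 × $7 = $201.50.

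**Table 1.** Twelve weeks counted from a CGM placement at day 7 end at day 7 + 84 = day 91. That is 12 paid weeks and $210, but it ends a week after a visit held at day 84.

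**Low adherence at 11 weeks.** A LOAN2DOSE participant who never doses but shares data loses $115.50 + $55 = $170.50 and keeps $39.50. The COIN2DOSE counterpart earns $22. The gap is again $17.50. Only a participant who also never shares data keeps exactly $17.50 in LOAN2DOSE, against $0 in COIN2DOSE.

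**Late visit 2.** Beyond day 91 the stated limits of $24 and $210 bind. The protocol does not say how extra days count once a limit is reached, so no gap is calculated here.

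**Trigger wording.** COIN2DOSE pays a window holding one or more carbohydrate-associated boluses. The literal complement is a window holding none. A window with one or more boluses missed is a different condition: a window with one bolused and one unbolused eating occasion would meet both.

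**The case against.** The strongest defence is that $210 is right and only the period is loosely worded. It reproduces exactly at 12 weeks, the $24 cap points to 12 weeks, and Section 6.0 equates the 12-week visit with 90 days. Table 1's count from CGM placement ends at about day 91, close to its 3-month visit. On that view the shortfall at a nominal visit is nearer $2.50 than $17.50. This largely stands. A reader might infer that $210 is an error, but the documents do not show that; the period wording may be what needs changing. What remains is that the paragraph's own period does not yield its own total, and the other sections do not settle the length.

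The defence can add that the two arms share rates, period wording and totals, so they mirror each other. That holds for the wording. It holds for the money only at 12 paid weeks, because one arm starts from zero and the other from a fixed sum.

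A reader might also infer that a late visit 2 lets deductions exceed the bank, or raises the maximum to $242.50 at day 104 (97 / 7 × $17.50). The stated $24 and $210 limits rule that out. Nor does a gain-versus-loss comparison become confounded in a planned test: the between-arm hypotheses in Section 2.2 set each active arm against control, and none compares COIN2DOSE with LOAN2DOSE.

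On the trigger, the shared meal windows and daily maximum, and the Study Summary's account of deductions for missed doses, make the intended meaning fairly clear. It is a wording point only.

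**Conclusion.** The point holds as an internal contradiction: $210 and the $24 cap fit only 12 paid weeks, while Section 5.0 literally gives 11, and other sections give 11 to 13 weeks, 90 days, or 12 weeks from CGM placement. The documents do not show which element is wrong.

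The maximum falls short by $17.50 on the literal reading ($192.50 against $210) and by $2.50 with visit 2 at day 90. Those sums are also the amounts by which LOAN2DOSE would pay more than COIN2DOSE for the same behaviour; at the early edge of the visit window the difference reaches $37.50. These figures assume a day-7 start, payment ending at visit 2, and pro-rating of part-weeks.

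The consequence is for the definition of the intervention and the amount promised to participants. No endpoint analysis, hypothesis test, power or sample-size figure depends on it. It should be corrected, since the payment is the intervention, but it does not threaten the pilot.

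**What to change.** - Reconcile Sections 1.0, 5.0 (both arms), 6.0 and Table 1 on one number of paid weeks. Which number is for the investigators to decide.
- State the maximum as $17.50 × that number ($192.50 for 11, $210 for 12). Use it for both the COIN2DOSE maximum and the LOAN2DOSE opening bank and maximum deduction.
- Set the data-sharing cap at $2 × the same number, and the Section 15.0 total at $120 plus the maximum.
- Say how an early or late visit 2, and any part-week, is handled, in the same terms for both arms.
- As a minor wording change, define the LOAN2DOSE per-meal deduction as applying to a mealtime window with no carbohydrate-associated bolus, so that it is the exact complement of the COIN2DOSE payment.

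The cost is a few sentences and, if the maximum changes, the same figures in the consent documents. If the reconciled period is 12 weeks, the dollar figures stay as they are. Between the 11- and 12-week readings, at most $17.50 per active-arm participant is at issue.
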